11.2.3 Exploratory efficacy variables

The exploratory endpoints are defined as follows:

- Achievement of a partial or complete overall response at 24 weeks post enrollment (per NIH Consensus Development Project response criteria)

Definitions for the efficacy endpoint are based on the draft 2014 NIH Consensus Guidelines [see Appendix 7].

Baseline or subsequent organ abnormalities that are not due to chronic GVHD are not evaluable for response (at the organ level).

Complete overall response definition:

A complete response is defined as resolution of all reversible manifestations due to chronic GVHD in the following organs at the Week 24 assessment, resulting in:

- Skin: NIH Skin Score of 0 after previous involvement
- Mouth: NIH Modified Oral Mucositis Score of 0 after previous involvement

- Liver: normal ALT, alkaline phosphatase, and TBL after previous elevation of one or more
- Upper GI: NIH Upper GI Score of 0 after previous involvement
- Lower GI: NIH Lower GI Score of 0 after previous involvement
- Esophagus: NIH Esophagus Score of 0 after previous involvement
- Lungs: normal FEV₁ absolute value after previous involvement (normalization to FEV₁ $\geq 80\%$ predicted is considered a complete response)
- Eyes: NIH Eye Score of 0 after previous involvement
- Joint/fascia: Both NIH Joint and Fascia Score of 0 and photographic range of motion (P-ROM) score of 25 after previous involvement by at least one measure
- Global: Clinician Overall Severity Score of 0

Partial overall response definition:

A partial overall response is defined as improvement in a measure for at least one organ without progression in measures for any other organ. The proposed general guideline for defining partial response in a specific organ requires a change in score from baseline as follows:

- Skin: decrease in NIH Skin Score by at least 1 point
- Mouth: decrease in Modified Oral Mucositis Score by at least 2 points
- Liver: decrease by 50% in ALT, alkaline phosphatase, or TBL
- Upper GI: decrease in NIH Upper GI Score by at least 1 point
- Lower GI: decrease in NIH Lower GI Score by at least 1 point
- Esophagus: decrease in NIH Esophagus Score by at least 1 point
- Lungs: increase by at least 10% predicted absolute value of FEV₁, as long as initial FEV₁ $< 70\%$ predicted
- Eyes: decrease in NIH Eye Score by at least 1 point
- Joint/fascia: decrease in NIH Joint and Fascia Score by 1 or more points or increase in P-ROM score by 1 or more points for any site
- Global: Clinician Overall Severity Score decreases by 2 or more points on a 0–10 scale

The proposed general guideline for defining progression in a specific organ requires a change in score from baseline as follows:

- Skin: increase in NIH Skin Score by at least 1 point, except from 0 to 1
- Mouth: increase in Modified Oral Mucositis Score by at least 2 points

Confidential

- Liver: increase by $\geq 2 \times$ ULN for ALT, alkaline phosphatase or TBL
- Upper GI: increase in NIH Upper GI Score by at least 1 point, except from 0 to 1
- Lower GI: increase in NIH Lower GI Score by at least 1 point, except from 0 to 1
- Esophagus: increase in NIH Esophagus Score by at least 1 point, except from 0 to 1
- Lungs: decrease by at least 10% absolute value of FEV₁, as long as final FEV₁ < 70% predicted
- Eyes: increase in NIH Eye Score by at least 1 point, except from 0 to 1
- Joint/fascia: increase in NIH Joint and Fascia Score by 1 or more points or decrease in P-ROM score by 1 or more points for any site
- Global: Clinician Overall Severity Score increases by 2 or more points on a 0–10 scale

The endpoint is reached if the subject is considered a partial or complete responder at Week 24. The remaining subjects will be considered as non-responders, this includes subjects with stable disease and subjects with mixed response (defined as complete or partial response in at least one organ accompanied by progression in another organ). Patients who discontinue the study prior to the Week 24 assessment are considered non-responders.

- Need for rescue therapy for chronic GVHD
 - Rescue therapy is the addition of any new systemic or topical IS therapy or exceeding baseline dose for any non-steroid IS or exceeding glucocorticoid dose equivalent to prednisone $> 1 \text{ mg/kg/day}$

This exploratory endpoint is defined as a binary endpoint. Subjects will be considered as responders in case no rescue therapy is administered; subjects will be considered as non-responders in case subjects received a rescue therapy during the treatment phase for at least one day. Every effort will be made to collect the concomitant medications data with complete start dates in order to make sure the endpoint is derived correctly. Patients who discontinue the study prior to the Week 24 assessment are considered non-responders.

- Partial or complete organ-specific response for the specific organ manifestation at Week 12 and Week 24 in subjects with a specific organ manifestation of chronic GVHD
 - Affected organs limited to 2014 NIH consensus criteria organs of skin, eyes, mouth, esophagus, upper GI, lower GI, liver, lungs, and joints and fascia

This endpoint is a binary sub-endpoint of the first exploratory endpoint (see above), split by organ. The endpoint will be derived in the same way as described above but at an organ level. The endpoint will be evaluated independently at the Week 12 and Week 24 assessment. Only organs with reversible manifestations will be included in the analysis.

Confidential

Only subjects with manifestations at baseline or subjects developing manifestations during the study at the corresponding organ will be included in the analyses of the sub-endpoints. Patients who discontinue the study prior to the Week 24 assessment are considered non-responders.

- Partial or complete overall response at Week 12

This binary endpoint is defined like the first exploratory endpoint (see above) but at the Week 12 assessment.

- Complete response at 24 weeks

A responder of this binary endpoint is defined as reaching a complete response at the Week 24 assessment. A non-responder is defined as reaching a partial or mixed response or no response (stable disease or progression) at the Week 24 assessment or dropping out of the study prior to the Week 24 assessment.

- Partial or complete overall response at latest evaluable assessment during the core study (Week 12 and Week 24)
- Average glucocorticoid daily dose over 24 weeks versus baseline dose

The average dose is defined as the sum of all doses of glucocorticoid received, adjusted by the time in days.

- Percent glucocorticoid dose at Week 24 versus baseline.

This exploratory endpoint is defined as the percentage of the glucocorticoid dose received at the Week 24 assessment compared to the dose received at baseline.

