6.3 Efficacy endpoints (exploratory)

The main efficacy endpoint is:

- Achievement of a partial or complete overall response at 24 weeks post-enrollment

Definitions for the efficacy endpoint are based on the draft 2014 NIH Consensus Development Project response criteria [NIH Therapeutic Response 2014]. Baseline or subsequent organ abnormalities that are not due to chronic GVHD are not evaluable for response (at the organ level).

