6.3.1 Complete overall response definition

A complete overall response is defined as resolution of all reversible manifestations due to chronic GVHD in the following organs at the Week 24 assessment, resulting in:

- Skin: NIH Skin Score of 0 after previous involvement
- Mouth: NIH Modified Oral Mucositis Score of 0 after previous involvement
- Liver: normal ALT, alkaline phosphatase, and TBL after previous elevation of one or more
- Upper GI: NIH Upper GI Score of 0 after previous involvement
- Lower GI: NIH Lower GI Score of 0 after previous involvement
- Esophagus: NIH Esophagus Score of 0 after previous involvement
- Lungs: normal FEV₁ absolute value after previous involvement (normalization to FEV₁ \geq 80% predicted is considered a complete response)

- Eyes: NIH Eye Score of 0 after previous involvement
- Joint/fascia: Both NIH Joint and Fascia Score of 0 and photographic range of motion (P-ROM) score of 25 after previous involvement by at least one measure
- Global: Clinician Overall Severity Score of 0

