6.3.2 Partial overall response definition

A partial overall response is defined as improvement in a measure for at least one organ without increase in measures for any other organ. A subject is considered as a partial responder at the Week 24 assessment, if there is a change of clinical benefit from baseline in at least one of the organs assessed (skin, mouth, liver, upper and lower GI, esophagus, lung, eye, and joint/fascia) and no progression in any other organ (stable NIH scores compared to baseline).

The proposed general guideline for defining partial response in a specific organ requires a change in score from baseline as follows:

- Skin: decrease in NIH Skin Score by at least 1 point
- Mouth: decrease in NIH Modified Oral Mucositis Score by at least 2 points
- Liver: decrease by 50% in ALT, alkaline phosphatase, or TBL
- Upper GI: decrease in NIH Upper GI Score by at least 1 point
- Lower GI: decrease in NIH Lower GI Score by at least 1 point
- Esophagus: decrease in NIH Esophagus Score by at least 1 point
- Lungs: increase by at least 10% predicted absolute value of FEV₁, as long as initial FEV₁ < 70% predicted
- Eyes: decrease in NIH Eye Score by at least 1 point
- Joint/fascia: decrease in NIH Joint and Fascia Score by 1 or more points or increase in P-ROM score by 1 or more points for any site
- Global: Clinician Overall Severity Score decreases by 2 or more points on a 0–10 scale

The proposed general guideline for defining progression in a specific organ requires a change in score from baseline as follows:

- Skin: increase in NIH Skin Score by at least 1 point, except from 0 to 1
- Mouth: increase in NIH Modified Oral Mucositis Score by at least 2 points
- Liver: increase by $\geq 2 \times$ ULN for ALT, alkaline phosphatase or TBL
- Upper GI: increase in NIH Upper GI Score by at least 1 point, except from 0 to 1
- Lower GI: increase in NIH Lower GI Score by at least 1 point, except from 0 to 1

- Esophagus: increase in NIH Esophagus Score by at least 1 point, except from 0 to 1
- Lungs: decrease by at least 10% absolute value of FEV₁, as long as final FEV₁ < 70% predicted
- Eyes: increase in NIH Eye Score by at least 1 point, except from 0 to 1
- Joint/fascia: increase in NIH Joint and Fascia Score by 1 or more points or decrease in P-ROM score by 1 or more points for any site
- Global: Clinician Overall Severity Score increases by 2 or more points on a 0–10 scale

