6.3.4 Other efficacy endpoints

Other efficacy endpoints include:

- Need for rescue therapy for chronic GVHD
 - Rescue therapy is the addition of any new systemic or topical IS therapy, or exceeding baseline dose for any non-steroid IS, or exceeding glucocorticoid dose equivalent to prednisone > 1 mg/kg/day
- Partial or complete organ-specific response for the specific organ manifestation at Week 12 and Week 24 in subjects with a specific organ manifestation of chronic GVHD at study baseline
 - Affected organs limited to 2014 NIH consensus criteria organs of skin, eyes, mouth, esophagus, upper GI, lower GI, liver, lungs, and joints and fascia
- Partial or complete overall response at 12 weeks post-enrollment
- Complete response at Week 24
- Partial or complete overall response at latest evaluable assessment during the core study (Week 12 and Week 24)
- Average glucocorticoid daily dose over 24 weeks versus baseline dose
- Percent glucocorticoid dose at Week 24 versus baseline

Confidential

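### The liver entry for partial response has no baseline-elevation condition, so a halving of a normal liver test can count as an overall partial response

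*Combined protocol and SAP*

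**What the plan says.** Section 6.3 names the main efficacy endpoint: "Achievement of a partial or complete overall response at 24 weeks post-enrollment". Section 11.2.3 gives the overall rule: "A partial overall response is defined as improvement in a measure for at least one organ without progression in measures for any other organ". Organ-level guidelines follow. For the liver, the partial-response entry is "Liver: decrease by 50% in ALT, alkaline phosphatase, or TBL", and the synopsis and Section 6.3.2 have the same entry.

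The neighbouring rules are tighter. Complete response in the liver requires "normal ALT, alkaline phosphatase, and TBL after previous elevation of one or more". Partial response in the lung applies only if initial FEV₁ was below 70% predicted. Liver progression requires a rise of at least 2 × ULN.

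The partial-response list also has an entry that is not an organ, "Global: Clinician Overall Severity Score decreases by 2 or more points", and the progression list has its mirror image. Section 6.3.2 says that improvement must occur "in at least one of the organs assessed (skin, mouth, liver, upper and lower GI, esophagus, lung, eye, and joint/fascia"), which is nine organs without the global score. Section 6.3.4 names the same nine for the organ-specific endpoint.

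**The concern.** Read literally, the liver entry is met when any one of three tests halves, whatever its starting value. An ALT that goes from 36 to 18 U/L in a subject with no liver involvement (illustrative values) would satisfy it. If no other organ progresses, that subject is an overall partial responder although no chronic GVHD manifestation has improved.

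Many subjects could be exposed. Liver is not among the qualifying organs in inclusion criterion 6, and exclusion criteria 13 and 14 remove subjects with markedly raised transaminases or bilirubin. The trial is open-label with one arm, so no control rate would reveal spurious responders. With 30 subjects, each one moves the rate by 1/30 = 3.3 percentage points. The same definition feeds the Week 12 and latest-assessment endpoints and the extension analyses.

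**Working it through.** **Does another provision close the gap?**

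- The note on abnormalities not due to chronic GVHD (Sections 6.3 and 11.2.3) makes those abnormalities non-evaluable. A normal value is not an abnormality.
- The limit to subjects with involvement of the organ, "in subjects with a specific organ manifestation of chronic GVHD at study baseline" in Section 6.3.4 and similar in Section 11.2.3, is attached to the organ-specific endpoint and not to overall response.
- The other organ measures cannot improve from normal: the 0–3 and 0–12 scores are already 0, P-ROM is already at its maximum, and lung has its FEV₁ condition.
- Liver progression gives no offset. Variation within the normal range can halve a test but cannot raise it by 2 × ULN.

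**Is there a plan figure to reproduce?** The plan gives no expected response rate and no power for this endpoint. Its only power figures, about 85% (30 subjects) and 75% (23), concern lymphocyte counts. A normal approximation for two independent groups (difference 0.35, SD √((0.6² + 0.4²)/2) = 0.51, one-sided 5%) returns 84.5% and 75.3%. Those figures do not bear on this point.

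**Chance that a stable subject halves a test.** The documents give no within-subject CVs, so these are assumptions. Under a log-normal model with no true change,

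P(one test halves) = Φ(ln 0.5 / (√2 · s)), with s = √ln(1 + CV²).

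| CV | s | P(halves) |
|---|---|---|
| 10% | 0.100 | about 0 |
| 15% | 0.149 | 0.05% |
| 20% | 0.198 | 0.67% |
| 25% | 0.246 | 2.3% |
| 30% | 0.294 | 4.75% |

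For any of three tests, taken as independent (ALT / alkaline phosphatase / bilirubin):

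- CVs 20/10/25%: 1 − (0.9933)(1.0000)(0.9767) = 3.0%
- CVs 30/15/30%: 1 − (0.9525)(0.9995)(0.9525) = 9.3%

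More extreme choices, 15/8/20% and 35/20/35%, give 0.7% and 15%.

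**How many subjects are exposed?** A false responder must have normal liver tests, not be a true responder, have no progression, and reach Week 24, because Section 11.2.3 counts earlier discontinuation as non-response. Assume 40% true response and 75% of non-responders without progression, and treat all of these as having normal tests, which leans high.

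- No dropout: 30 × 0.60 × 0.75 = 13.5 exposed. At 3.0% to 9.3% this gives 0.4 to 1.3 extra responders.
- 25% dropout (the scenario in Section 11.4), all dropouts taken as non-responders: (18 − 7.5) × 0.75 = 7.9 exposed. This gives 0.2 to 0.7.

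The combined range is about 0.2 to 1.3 extra responders in 30, or roughly 1 to 4 percentage points.

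**The case against.** Section 6.3.2 asks for a clinically beneficial change in an organ, and a fall within the normal range is hard to call that. The lists are offered as general guidelines, Section 11 leaves derivation algorithms to the SAP, and the criteria follow a draft consensus standard that cannot be consulted here. A gate might therefore exist in the programmed rule, or its absence might follow the standard. This tempers the point but does not remove it: clinical benefit is undefined, the term does not appear in Section 11.2.3, and the stated rule has no gate in any of its three places.

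Section 1.3.2.4 reports transaminase elevations on ponesimod, and Section 8.2.6 places the end-of-treatment visit 1 to 3 days after the last dose. Halving of a normal ALT may thus be rarer than modelled. This stands. If ALT contributed nothing, the per-subject range would fall to about 2.3% to 4.8%, almost all from bilirubin.

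A reader might infer two stronger things. The first is that 3% to 9% of all 30 subjects, about 1 to 3, would be false responders. That ignores true responders, subjects with progression and dropouts, none of whom can be falsely added. The second is that a 2-point fall in the unblinded clinician rating alone makes a responder and so also inflates the rate. The documents do not support this: Section 11.2.3 requires improvement in an organ, and the nine organs in Section 6.3.2 exclude the global score. What remains is an ambiguity, because the entry sits under a heading about specific organs and Section 11.2.3 does not repeat the nine-organ list for overall response. If the score were counted, its mirror progression entry could also cancel responses, so no direction can be claimed.

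**Conclusion.** The liver point holds. As stated, the rule can classify a subject with normal liver tests and stable disease as an overall partial responder, and for such subjects it can only push the rate upward. The size is modest: about 0.2 to 1.3 extra responders in 30. That rests wholly on assumed CVs, independence of the three tests, 40% true response, 75% of non-responders without progression, and 0–25% dropout. The documents supply none of these except the dropout scenario.

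The endpoint is exploratory and summarised descriptively, with no test or threshold, so the effect is on how the rate is read. The primary pharmacodynamic analysis, its power and the sample size are unaffected. The global-score entry needs clarification only.

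**What to change.** In the synopsis, Section 6.3.2 and Section 11.2.3, limit the liver partial-response entry to a test that was above ULN at baseline because of chronic GVHD, in line with the complete-response rule. With that condition, false qualification from normal baseline tests falls to zero.

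In Section 11.2.3, repeat the nine-organ list from Section 6.3.2 for overall response and state that the Clinician Overall Severity Score does not by itself create or cancel an overall response. Report that score separately.

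The cost is a few sentences before database lock and no new data, since the liver tests and their ULNs are already collected. The reported response rate may be slightly lower.

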11.2.8 Analysis of the efficacy variables

The analyses of all exploratory endpoints will be based on the PPS and FAS, if applicable. The following binary endpoints will be summarized descriptively as described in Section 11:

- Achievement of a partial or complete overall response at 24 weeks (per NIH Consensus Development Project response criteria)
- Need for rescue therapy for chronic GVHD
- Partial or complete organ-specific response for the specific organ manifestation at Week 12 and Week 24 in subjects with a specific organ manifestation of chronic GVHD
- Partial or complete overall response at Week 12
- Complete response at Week 24
- Partial or complete overall response at latest evaluable assessment during the core study (Week 12 and Week 24)

The remaining two exposure-related, continuous endpoints will be analyzed based on summary statistics as described in Section 11:

- Average glucocorticoid daily dose over 24 weeks versus baseline dose
- Percent glucocorticoid dose at Week 24 versus baseline

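### Section 11.2.3 adds subjects with new on-study organ involvement to the organ-specific response denominator, against Section 6.3.4 and the synopsis; the rate usually falls but can rise

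*Combined protocol and SAP*

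**What the plan says.** Section 6.3.4 defines partial or complete organ-specific response "in subjects with a specific organ manifestation of chronic GVHD at study baseline", and the efficacy endpoints in the synopsis carry the same restriction.

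Section 11.2.3 leaves the reference to baseline out of the endpoint's name and then widens the population: "Only subjects with manifestations at baseline or subjects developing manifestations during the study at the corresponding organ will be included in the analyses". The endpoint names in Sections 11.2.8 and 11.2.9 also omit the restriction to baseline.

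On derivation, Section 11.2.3 says: "The endpoint will be derived in the same way as described above but at an organ level". The rules it points back to are of two kinds. Partial response in an organ "requires a change in score from baseline as follows", followed by a list of decreases. Complete response is an end state, for example "Skin: NIH Skin Score of 0 after previous involvement" and "Lungs: normal FEV₁ absolute value after previous involvement". On timing: "The endpoint will be evaluated independently at the Week 12 and Week 24 assessment".

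Section 11.2.8 gives the status of the analysis: "The following binary endpoints will be summarized descriptively as described in Section 11". No test is attached.

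**The concern.** The two sections give different answers to who is counted, and nothing says which governs. Under Section 11.2.3, membership of the denominator is decided by an on-treatment event. The resulting percentage mixes two quantities: how often existing organ disease responds, and how often new organ disease appears. There is one arm, so no control group shares the distortion.

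The added subjects also fit the response rules poorly. For skin, eyes, esophagus and upper and lower GI, Section 11.2.3 expressly does not treat a rise from 0 to 1 as progression. Yet that same rise brings the subject into the organ's denominator, where he or she counts as a non-responder for as long as it lasts. No text says how a new-onset subject is to be classified. Nor is it stated whether a subject first involved after Week 12 belongs in the Week 12 denominator.

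At stake is the reading of each organ's response rate in a first study of the drug in this disease.

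**Working it through.** The documents give no expected rate or count for this endpoint, so there is no planned figure to reproduce. The check has two parts: what the rules allow for a new-onset subject, and how far such subjects can move the rate.

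**Partial response.** In the organs scored from 0 (skin, mouth, eyes, esophagus, upper and lower GI, and the joint and fascia score), partial response needs a decrease from baseline of at least 1 point, or 2 for the mouth. From a baseline of 0 no decrease is possible. The joint rule also accepts a gain in range of motion, but a subject at the normal maximum of 25 has nothing to gain. So a new-onset subject cannot be a partial responder in these organs. If the manifestation is still present at the assessment, complete response is excluded too, and the subject is a non-responder.

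**Complete response.** The rule asks for a score of 0 following earlier involvement and does not say that the involvement was present at baseline. Table 1 schedules Form A on Day 1, at Week 12 and at Week 24. A subject scoring 0 on Day 1, 1 or more at Week 12 and 0 at Week 24 literally meets the rule at Week 24, with no net change from baseline.

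**Liver and lung.** These are judged on liver tests and FEV₁, so the argument from a zero score does not carry over. Both are also measured at Weeks 4 and 8, so onset followed by resolution is possible by Week 12.

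**Formula.** Let B be the subjects involved at baseline, R the responders among them, k the new-onset subjects added, and c those of the k counted as complete responders.

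- Section 6.3.4 rate: R/B
- Section 11.2.3 rate: (R + c)/(B + k)

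The second is lower than the first when B(R + c) < R(B + k), that is, when c/k < R/B. It is higher when c/k > R/B.

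**Numbers.** The counts are assumed: B = 20, R = 8, so R/B = 8/20 = 40.0%.

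| k added | none counted (c = 0) | all counted (c = k) |
|---|---|---|
| 1 | 8/21 = 38.1% | 9/21 = 42.9% |
| 2 | 8/22 = 36.4% | 10/22 = 45.5% |
| 3 | 8/23 = 34.8% | 11/23 = 47.8% |
| 5 | 8/25 = 32.0% | 13/25 = 52.0% |

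For a less commonly involved organ, B = 10 and R = 4 also gives 40.0%. With k = 3 the range is 4/13 = 30.8% to 7/13 = 53.8%.

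**Extension.** Section 11.2.5 carries the definitions over with EX-1 as baseline, and Section 11.2.9 assesses this endpoint at Weeks 12, 24 and 96. A longer period gives more opportunity for new involvement, so k can be larger there.

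**The case against.** A reader might infer that new-onset subjects can never count as responders and that the rate is therefore always diluted. The documents do not support that. It is true of partial response in the scored organs, but the complete-response wording leaves a route into the numerator, and liver and lung have no zero baseline. The direction depends on c/k against R/B.

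It can also be said that the larger shifts are unlikely. With 30 subjects planned and 20 involved at baseline in an organ, only 10 remain at risk of new onset there; k = 5 means that half of them develop it. Nothing in the documents supports so high a rate. With one or two such subjects and no responders among them, the rate falls by about 2 to 4 points. This stands, and it is why the result is given as a range.

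Finally, the endpoint is one exploratory, descriptive summary with no test or threshold. Section 11 says that all data will be listed, so the baseline-involved rate could be recovered from the listings. That limits the weight of the point. It does not settle which rate is to be tabulated, and the two sections still disagree.

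**Conclusion.** The conflict is real: Section 11.2.3 defines a wider denominator than Section 6.3.4 and the synopsis, and Sections 11.2.8 and 11.2.9 do not resolve it. Dilution is the usual effect, because a new manifestation still present at the assessment is a certain non-response in the scored organs. Upward bias is possible where an on-study onset resolves and is counted as complete response.

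In the main illustration, a 40.0% rate becomes anything from 32.0% to 52.0% with up to five new-onset subjects. These figures rest on assumed counts and on the two extremes of classification, none or all counted; they show how far the rate can move and do not forecast it. The consequence is confined to the exploratory organ-level summaries in the core and extension periods. The primary pharmacodynamic analysis and the sample size are unaffected.

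**What to change.** In Sections 11.2.3, 11.2.8 and 11.2.9, restrict the organ-specific denominator to subjects with that organ's manifestation at baseline, as in Section 6.3.4, with EX-1 as the baseline for the extension. Report new on-study organ involvement as a separate count per organ and visit, so that no information is lost. This also removes the open questions about how new-onset subjects are classified and when they enter the denominator.

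The cost is about one sentence in each of the three sections and one extra tabulation from data already collected. Section 11 has the SAP approved before database lock, so the change can be made before then.
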